#### **7.6.16 Clinical Laboratory Tests**

Blood samples for assessment of the following parameters will be obtained at the baseline visit and all M0 Phase visits unless otherwise noted:

- Alkaline phosphatase
- Hemoglobin
- Lactate dehydrogenase (LDH)
- Serum albumin
- Serum PSA
- Testosterone (baseline visit only)

Local laboratories will be used for the above laboratory tests and the results will be recorded on the eCRF.

At each time point for data collection during M0 phase and M1 phase, clinical laboratory (alkaline phosphatase, hemoglobin, LDH, serum albumin) and serum PSA data that have become available since the previous time point will be recorded in the eCRF. Blood samples for clinical laboratory or serum PSA values will not be collected during M1 Phase.

#### **7.6.17 Additional Optional Research for Biomarkers**

Patients will be given the opportunity to consent to allow Dendreon to collect investigational blood samples for use in AOR, which will include biomarker analysis and other additional testing. The samples will be analyzed for biomarkers that may be predictive of treatment effects and/or prognostic for MFS, OS, or an imaging study positive for metastatic disease. The samples will be retained for an indefinite period of time. They may be used for gene and gene expression analysis, and retained samples may be sent to outside laboratories for testing. Retained samples will be used for research only, and will not be sold. AOR blood samples will not be identified using patient names or other personal identifiers. Neither the patient nor the study site will receive AOR testing results.

For patients who provide consent for AOR, a whole blood sample will be obtained at the baseline visit and each M0 Phase visit (at scheduled 6-month M0 Phase study visits and M0 Phase imaging visits [within  $\pm$  1 month]) until diagnosis with M1 CRPC, or the M0 Phase patient completes or is discontinued from the study. Such samples will not be collected from patients who do not provide additional consent for AOR.

#### **7.6.18 Serious Adverse Events**

The collection of adverse events (AEs) will be limited to SAEs in patients who receive at least 1 partial ( $> 0$  mL) infusion of Provenge during the study and that occur at any time from the first infusion through 30 days after the last infusion, regardless of relationship to Provenge.

Any patient who is not diagnosed with M1 CRPC and receives at least 1 partial ( $> 0$  mL) infusion of Provenge during the study will be withdrawn from the study. Serious adverse events that occur in such patients will be recorded as described above.

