### **7.1 Baseline Visit**

The baseline visit will occur  $\leq$  28 days after written informed consent is obtained and include the following:

- Demographics and medical history, including prior and current medical conditions or illness, and allergies to medications.
- Date of diagnosis with CRPC, with confirming serum PSA values and associated hormonal therapy.
- Confirmation of no current or prior treatment with investigational therapy for M0 CRPC, Taxotere (docetaxel), Provenge® (sipuleucel-T), Zytiga (abiraterone acetate), Xtandi (enzalutamide), Jevtana (cabazitaxel), or Xofigo (radium Ra 223 dichloride).
- Prostate cancer imaging study history.
- Confirmation that no imaging study to determine the presence of bone or soft tissue metastases was performed  $\leq$  3 months prior to the date written informed consent was obtained.
- ECOG performance status.
- Height and weight.
- ACE-27.
- Gleason score.
- Serum PSA history.
- Current opioid analgesic use (yes/no).
- Concomitant medications (prescription medications only).
- Pain status (with BPI).
- Previous and ongoing prostate cancer interventions. Prostate cancer interventions include but are not limited to radiation, chemotherapy, hormonal therapy, investigational cancer therapies, all other systemic therapies (including steroids), and surgery for prostate cancer. Record indication(s) for choice of therapy, starting dose, timing (start and stop dates), and rationale for starting and stopping therapy (e.g., PSA progression) on the eCRF.
- Bone and soft tissue imaging studies for detection of metastatic prostate cancer.
- Blood sample for clinical laboratory tests at local laboratory, as indicated in the Schedule of Assessments ([Table 1](#)).
- Blood sample for biomarker analysis, providing the patient has consented to AOR.

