##### Definition of a Serious Adverse Event

An SAE is defined as any adverse drug experience occurring at any dose that results in any of the following outcomes: death, a life-threatening adverse drug experience, inpatient hospitalization or prolongation of existing hospitalization, a persistent or significant disability/incapacity, or a congenital anomaly/birth defect. Important medical events that may not result in death, be life-threatening, or require hospitalization may be considered

SAEs when, based upon appropriate medical judgment, they may jeopardize the patient and may require medical or surgical intervention to prevent one of the outcomes listed in this definition. Examples of such medical events include allergic bronchospasm requiring intensive treatment in an emergency room or at home, blood dyscrasias or convulsions that do not result in inpatient hospitalization, or the development of drug dependency or drug abuse.

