#### Categories for Ranking the Relationship of a Serious Adverse Event

*None:* The SAE is clearly related to other factors, such as the patient's clinical state, environmental factors, or other modes of therapy or concomitant drugs administered to the patient.

*Possible:* The SAE follows a reasonable temporal sequence from a study-required procedure or administration of Provence, but could readily have been produced by the patient's clinical state, environmental factors, or other modes of therapy or concomitant drugs administered to the patient.

*Probable:* The SAE follows a reasonable temporal sequence from a study-required procedure or administration of Provence and cannot readily have been produced by the patient's clinical state, environmental factors, or other modes of therapy or concomitant drugs administered to the patient.

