## Expedited Reporting Requirements

Dendreon will notify the FDA or other applicable regulatory agencies and health authorities of any SAE in this study associated with the use of Provenge that is unexpected and at least possibly related. Such notification will be provided within 15 calendar days after Dendreon's initial receipt of the information for all SAEs.

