#### **8.4 Safety Events**

In this study, the collection of AEs will be limited to SAEs and meeting the criteria defined in Section 7.6.18. Serious adverse events will be summarized and listed by the Medical Dictionary for Regulatory Activities (MedDRA) preferred term within each system organ class. Serious adverse events that occur multiple times for a patient will be counted only once per patient in incidence summary tables. A listing of SAEs at least possibly related to Provenge will be provided.

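### SAEs related to study-required procedures are not collected outside the Provenge window, and inside it one merged causality grade cannot separate the procedure from Provenge

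*Combined protocol and SAP*

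**What the plan says.** **Who and when.** Section 7.6.18 sets the scope: "The collection of adverse events (AEs) will be limited to SAEs in patients who receive at least 1 partial" infusion of Provenge, covering any "time from the first infusion through 30 days after the last infusion, regardless of relationship to Provenge". The Synopsis, Sections 7.3 to 7.5 and Table 1 footnote j carry the same restriction. Table 1 marks Safety Events for the M0 and M1 Phase columns and leaves the baseline column empty.

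**What counts.** "An SAE is defined as any adverse drug experience occurring at any dose" with one of the usual serious outcomes. Procedures are not mentioned in the definition.

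**How causality is rated.** There is one scale: *None*, *Possible*, *Probable*. The upper two categories share an opening: "The SAE follows a reasonable temporal sequence from a study-required procedure or administration of Provence" (the product name is misspelt there).

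**Where the grade is used.** Section 8.4: "A listing of SAEs at least possibly related to Provenge will be provided". The expedited reporting paragraph gives 15 calendar days for "any SAE in this study associated with the use of Provenge that is unexpected and at least possibly related".

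**What the study requires.** Section 7.1 lists "Bone and soft tissue imaging studies for detection of metastatic prostate cancer" for every patient at baseline. Section 7.6.16 adds blood samples at baseline and all M0 Phase visits. Section 7.6.15 adds a more sensitive scan after an equivocal bone scan. It also adds a sponsor-paid repeat with the previous modality when M1 is found at first use of a more sensitive one.

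The statistical analysis plan was not finalized, so no later document settles these points.

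**The concern.** The study gives no treatment, so the risks it adds itself come from the procedures it requires. The authors evidently expected some SAEs to be attributed to those procedures, because the scale names them. The collection rule is tied to a product that the study does not supply, and it opens after most of the required procedures have been done. The definition of an SAE points to drugs alone. These three parts of Section 7.6.18 do not fit together.

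Two consequences follow. A serious event caused by a required scan in a man who has not started Provenge produces no protocol-specified SAE report to the sponsor. And where such an event does fall inside the window, its grade does not show which cause the investigator had in mind, so a listing and a regulatory trigger meant for Provenge can pick up something else.

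**Working it through.** The plan gives no figure on this point, so the check is a comparison of passages followed by an illustrative count.

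**Step 1. Place each required procedure against the window.**

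| Procedure | Source | Position relative to a first infusion |
|---|---|---|
| Baseline bone and soft-tissue imaging | 7.1, 7.6.15 | Before: prior Provenge is excluded (5.2.5) |
| Baseline blood draw | 7.6.16 | Before, same reason |
| Blood draws at M0 Phase visits | 7.6.16 | Before: a patient without M1 who receives Provenge is withdrawn (5.3) |
| Confirmatory scan after an equivocal bone scan | 7.6.15 | Normally before: it serves to establish M1 status |
| Repeat scan with the previous modality, within 1 month after the positive study | 7.6.15 | Can overlap: M1 is already diagnosed |
| M1 Phase blood draws | 7.6.16 | None are required |

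Only the repeat scan, or a late effect of an earlier procedure, has a realistic chance of falling inside the window.

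**Step 2. Follow two events through the rules.**

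*Event A: a serious reaction to the baseline scan in a man who has not received Provenge.* The collection rule is not met. The reporting paragraph of 7.6.18 covers only SAEs that meet the collection criteria, so no report is made and the procedure half of the scale is never applied.

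*Event B: a serious reaction to the repeat scan in a man who has started Provenge.* The event is collected, because the window is all-causality. *None* requires that other factors clearly explain the event, and its examples do not include study procedures. *Possible* and *Probable* are both satisfied by temporal sequence from the procedure alone. The grade is therefore *Possible* or *Probable* even if nobody suspects Provenge. Section 8.4 and the expedited paragraph both turn on at least possible relatedness, and the protocol specifies no second rating from which relatedness to Provenge could be read.

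**Step 3. Size of the uncollected part at baseline (illustrative).**

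- Patients: at least 2000 planned (8.1).
- Imaging procedures per patient: 1 to 2. Section 7.6.15 names MRI as an example for both bone and soft tissue, so one session may serve both (assumption).
- Procedures: 2000 × 1 = 2000 to 2000 × 2 = 4000.
- Serious procedure-related event rate: not in the documents; assumed 1 to 10 per 10,000.
- Expected events: 2000 × 0.0001 = 0.2 to 4000 × 0.001 = 4.0.
- Chance of at least one: 1 − (1 − 0.0001)^2000 = 0.18 to 1 − (1 − 0.001)^4000 = 0.98.

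Blood draws and later scans are not counted.

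**Step 4. Size of the misattributed part.** This cannot be computed: the documents give neither Provenge uptake nor the frequency of modality changes. Event B needs a change to a more sensitive modality, a positive result at first use, a repeat scan, Provenge started, and a scan-related SAE inside the window. The count must be very small.

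**The case against.** Restricted collection is a consistent and deliberate choice. It is stated the same way throughout, the study has no investigational product, and no objective concerns safety. The empty baseline cell in Table 1 follows from the rule and is not an oversight. Imaging uses each site's standard-of-care modality, and post-baseline imaging in the M0 Phase is otherwise at the investigator's discretion.

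Much of this stands, but it does not explain why the causality scale rates study-required procedures. Standard of care governs the choice of modality, not whether the baseline scan happens: every man must have it, and men imaged within the previous 3 months are excluded (5.2.2). The protocol therefore prompts a new scan.

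Three stronger readings are tempting, and the documents do not support them.

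- *Procedure-related SAEs are never captured.* Inside the window all SAEs are recorded whatever their cause. Section 7.6.14 records deaths and their cause for all patients, though not as SAEs.
- *Procedure-related events are necessarily sent to the Provenge listing.* Section 8.4 and the expedited paragraph each carry their own Provenge qualifier, and the latter also requires that the event be unexpected. The SAE Report Form is not in the documents and may ask about the two causes separately. The supportable claim is that such events can reach these outputs.
- *The sponsor or IRB has no way of learning about such events.* Investigators report study progress to the IRB (2.2), and monitors may read complete medical records (10.4). These routes are generic; what is missing is a specified SAE route.

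**Conclusion.** The concern holds in limited form. SAEs related to required procedures are not collected outside the Provenge window, although the protocol's own scale provides for rating them and its definition does not reach non-drug events. Inside the window, the single grade does not separate procedure from product, so the Section 8.4 listing and the 15-day trigger can include procedure-related events.

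The size is small. The uncollected part at baseline is about 0.2 to 4 events, resting entirely on an assumed rate and the planned minimum of 2000 patients. The misattributed part is a very small subset that cannot be quantified. Whether misattribution would occur in practice depends partly on an SAE form that is not available. The primary endpoint, the other endpoints and the sample size are untouched. This is an inexpensive improvement to safety reporting, not a threat to the study's conclusions.

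**What to change.** Reconcile the collection rule, SAE definition, relationship categories and expedited reporting paragraph in 7.6.18 with Section 8.4.

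1. **Main change.** Record two relationship grades for each SAE, one for the study-required procedure and one for Provenge. State that only the Provenge grade feeds the 8.4 Provenge listing and the expedited trigger. This repairs both outputs even if the sponsor keeps the present collection scope.
2. **Additional change.** From consent, and for a stated period after each required procedure, also collect SAEs judged at least possibly related to that procedure. Extend the SAE definition to cover them, since otherwise a non-drug injury would still fall outside it. Add a baseline Safety Events entry to Table 1 and a separate listing in 8.4. Leave the all-causality Provenge window as it is.
3. **Tidying.** Sections 7.3 to 7.5 and Table 1 footnote j give only the end of the Provenge window, while 7.6.18 gives both ends. Align them, and carry the changes into the Synopsis.

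Cost: a protocol amendment with IRB approval (2.2), possibly a revised consent form (2.1), one extra form field, one short listing, brief site training and a small number of extra SAE reports. That number depends on an event rate the documents do not give.

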##### Definition of a Serious Adverse Event

An SAE is defined as any adverse drug experience occurring at any dose that results in any of the following outcomes: death, a life-threatening adverse drug experience, inpatient hospitalization or prolongation of existing hospitalization, a persistent or significant disability/incapacity, or a congenital anomaly/birth defect. Important medical events that may not result in death, be life-threatening, or require hospitalization may be considered

SAEs when, based upon appropriate medical judgment, they may jeopardize the patient and may require medical or surgical intervention to prevent one of the outcomes listed in this definition. Examples of such medical events include allergic bronchospasm requiring intensive treatment in an emergency room or at home, blood dyscrasias or convulsions that do not result in inpatient hospitalization, or the development of drug dependency or drug abuse.

#### Categories for Ranking the Relationship of a Serious Adverse Event

*None:* The SAE is clearly related to other factors, such as the patient's clinical state, environmental factors, or other modes of therapy or concomitant drugs administered to the patient.

*Possible:* The SAE follows a reasonable temporal sequence from a study-required procedure or administration of Provence, but could readily have been produced by the patient's clinical state, environmental factors, or other modes of therapy or concomitant drugs administered to the patient.

*Probable:* The SAE follows a reasonable temporal sequence from a study-required procedure or administration of Provence and cannot readily have been produced by the patient's clinical state, environmental factors, or other modes of therapy or concomitant drugs administered to the patient.

#### Reporting Requirements for a Serious Adverse Event

Serious adverse events that meet the criteria for collection during the study, as outlined in this section, will be reported to Dendreon or designee. Serious adverse events must be reported to Dendreon or designee within 24 hours of first knowledge of the event by completing the SAE form. The SAE information must be reported to Dendreon or designee within 24 hours by telephone or facsimile, and a completed written report using Dendreon's SAE Report Form must be submitted by facsimile within 3 business days to:

Dendreon Corporation  
Attn: Safety Manager  
[contact]  
[contact]  
Email: [[contact]](mailto:[contact])  
Telephone (24-hour access): [contact]

Significant new information regarding an ongoing SAE and the resolution must be sent to Dendreon or designee within 3 business days of awareness of the new information on the SAE Report Form.

## Expedited Reporting Requirements

Dendreon will notify the FDA or other applicable regulatory agencies and health authorities of any SAE in this study associated with the use of Provenge that is unexpected and at least possibly related. Such notification will be provided within 15 calendar days after Dendreon's initial receipt of the information for all SAEs.

## **8.0 STATISTICAL METHODS**

### **8.1 Sample Size Considerations**

This study will identify patient characteristics at the time of the baseline imaging study that are predictive of an imaging study positive for M1 in patients with CRPC and no known M1. A minimum of 2000 patients will be registered in this study. This sample size is based on the following considerations.

The primary endpoint for the study will be the occurrence of a positive imaging study for M1 at baseline (yes or no), a binary variable. All patients with a baseline imaging study will be included in the analysis of the primary endpoint. Yu et al (2012) found that 32% of 2577 men screened for a trial enrolling patients with CRPC thought to be M0 did, in fact, have M1 CRPC, and it is anticipated that this study will have a similar finding. With 1000 patients at each of the 2 possible levels of a binary variable, for a total of 2000 patients, the variable is detectable with an odds ratio of 1.312 with 80% power using a 2-sided test at alpha = 0.05, assuming an imaging study positive for M1 at baseline in 34.95% and 29.05% of patients in level 1 and level 2 of the binary variable, respectively. However, a binary variable that is distributed at a ratio of 1:5 at baseline would allow for an odds ratio of 1.422 to be detected with 80% power assuming an imaging study positive for M1 at baseline in 38.5% and 30.6% of the patients in level 1 and level 2 of the binary variable, respectively.

### **8.2 General Considerations**

#### **8.2.1 Analysis Populations**

The all-enrolled population will include all patients registered in the study. The primary analysis will be based on the primary analysis population, which will include patients in the all-enrolled population who undergo a baseline imaging study. In addition, patients with M0 or M1 CRPC at baseline (M0 or M1 populations, respectively) will form separate analysis populations to address different questions of interest.

#### **8.2.2 Interim Analysis**

No formal interim analysis is planned for this study. Periodic summarization of the data will be performed on an ongoing basis. However, as there are no formal hypotheses being tested in this protocol, no significance-level adjustments will be made for statistical testing or estimation procedures that may be utilized.

### **8.2.3 Control Groups**

There is no reference product in this protocol. Descriptive comparisons may be made to external datasets.

## **8.3 Analysis of Endpoints**

### **8.3.1 Primary Endpoint**

The primary endpoint for the study will be the occurrence of an imaging study at baseline that is positive for M1 (yes or no) among all patients enrolled with a baseline imaging study.

Logistic regression analyses will be used to analyze the primary endpoint. Univariate logistic regression analyses will be performed separately for each variable of interest. A multivariate logistic regression analysis will be performed including all variables of interest. A stepwise regression model selection procedure will be used to identify a model that includes explanatory factors that are independently predictive of the occurrence of a positive imaging study. The logistic regression model will be used to develop a formula for predicting the probability of a positive imaging study given specific values for the variables included in the final model.

Variables that will be considered for inclusion in the model are age, race, ethnicity, duration of disease in years from initial diagnosis to study registration, total Gleason score at diagnosis, post-RP Gleason score total, baseline ECOG performance status, baseline hemoglobin, baseline alkaline phosphatase, baseline LDH, baseline serum albumin, baseline testosterone, baseline serum PSA, baseline PSADT, first serum PSA demonstrating CRPC, baseline body mass index (BMI), prior systemic therapy (yes or no), prior ADT (yes or no), prior RP (yes or no), and prior orchiectomy (yes or no), current opioid analgesic use (yes/no), and number of prior scans. Baseline BPI scores, including worst pain in last 24 hours, least pain in last 24 hours, average pain in last 24 hours, and pain right now, will also be considered for inclusion.

The above list of variables will be considered for inclusion in the final model; however, each variable will be initially screened and will be dropped from consideration for inclusion in the final model if it is shown to have little predictive value as a univariate predictor. Candidate variables for the final model will be determined by the following algorithm. A univariate logistic regression will be applied for each individual variable and all variables with  $p < 0.25$  will be considered as candidate variables for the final model. Interaction terms will also be considered for the final model. Interaction terms will be considered as candidates for the final model if the  $p$ -value for the interaction term is less than 0.25 from a model with predictor variables of variable a, variable b, and interaction of variable a and b. Only variables with  $p < 0.25$  from the univariate model screening procedure as discussed above will be considered for determining the list of interaction terms for consideration in the final model.

All candidate variables, including interaction terms identified by the algorithm discussed above, will be entered into the stepwise model selection procedure. The criteria for a variable to enter the model will be  $p < 0.05$  and variables will be retained in the model during the elimination step if  $p < 0.10$ . The final model will include all terms identified from the stepwise selection procedure and will also include all main effect terms for any interaction variables identified in the stepwise model selection procedure.

Although the above list of variables for consideration for inclusion in the model is a comprehensive one, addition or deletion of variables for consideration may occur. Therefore, the complete list of candidate variables for inclusion in the model will be provided in the final statistical analysis plan.

